8.2 SAFETY AND OTHER ASSESSMENTS

Demographics: Subject demographic information will be collected at the Screening Visit, including date of birth (or age), sex, race/ethnicity, native language, and highest education level.

Medical history: Medical and surgical history, prior and concurrent medications including cholinesterase inhibitor and memantine use, and current medical conditions will be recorded at the Screening Visit. Medical history will include history of cognitive impairment and psychiatric history.

Height and weight: Height will be measured at the Screening Visit. Weight will be measured at every visit except Visit 11 (the interim cognitive testing visit).

Vital signs: Temperature, blood pressure, heart rate, and respiratory rate will be assessed at the Screening Visit, prior to every infusion, 1 hour and 2 hours after the first infusion (Visit 1), 1 hour after every subsequent infusion (Visits 2 through 10 and 12 through 17), and at Visits 11, 18, and 19.

Physical and neurological examination: Physical and neurological examination will be performed by a study physician at the Screening Visit, Visit 11, Visit 18, and Visit 19.

Modified Hachinski Ischemia Score (MHIS): The Rosen-Modified Hachinski Ischemia Score (MHIS) is a tool to identify the possibility of a vascular etiology for a subject's cognitive impairment (Rosen et al. 1980). It will be performed by a study physician at the Screening Visit.

Geriatric Depression Scale (GDS): The Geriatric Depression Scale (GDS) (15 point version) is a screening assessment tool for depression specifically designed for older people (Sheikh and Yesavage 1986). A score of 5 or higher is suggestive of depression. It will be performed at the Screening Visit.

Electrocardiogram (ECG): 12-lead ECG will be obtained for screening purposes only at the Screening Visit.

Blood tests: Blood tests to be collected at the Screening Visit will include complete blood count (CBC), comprehensive metabolic panel (CMP), prothrombin time (PT)/international normalized ratio (INR), activated partial thromboplastin time (APTT), thyroid-stimulating hormone (TSH), vitamin B12 level, hepatitis B surface antigen (HBsAg), hepatitis B core antibody (HBcAb), hepatitis C virus antibody (HCVAb), and human immunodeficiency virus antigen/antibody screen (HIVAg/Ab). Blood samples will be obtained at Visit 1, prior to the first infusion, for type and screen and flow cytometry. After the first dose, subjects will have a CBC performed within 48 hours prior to each subsequent infusion (Visits 2 through 10 and 12 through 17). Additional safety laboratory monitoring will include a CMP every 4

weeks (Visits 4, 8, 10, 13, 15, and 17). CBC and CMP will also be obtained 12 weeks after the final dose (Visit 19).

Brain MRI: Brain MRI will be performed within the screening period and at Visit 18. MRI acquisition will be performed on a 3T MRI scanner (Siemens MAGNETOM Prisma). The sequences obtained will include proton magnetic resonance spectroscopy (¹H-MRS) from a mid-sagittal oblique 10.8 cm³ (2 × 2 × 2.7 cm) voxel in the region of the precuneus and posterior cingulate cortex.

Amyloid PET scan of brain: An amyloid PET scan may be performed within the screening period to confirm deposition of amyloid in the brain. A historical amyloid positive PET scan may be used provided that the scan and result are considered acceptable by the investigator.

Concomitant medications: Concomitant medications will be recorded at the Screening Visit and reviewed and updated at Visits 1-19.

Adverse events review: Subjects and study partners will be asked about adverse events at Visits 1-19. Adverse events will also be assessed if they are reported at any other time during the study by the subject or study partner, in person or by telephone.

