1.2 SCHEMA

1.3 SCHEDULE OF ACTIVITIES (SOA)

	Screening Dav.-60 to -1	Baseline Visit 1, Dav.1	Study Visit 2 Dav.8 +/-1 dav	Study Visit 3 Dav.15 +/-1 dav	Study Visit 4 Dav.22 +/-1 dav	Study Visit 5 Dav.29 +/-1 dav	Study Visit 6 Dav.36 +/-1 dav	Study Visit 7 Dav.43 +/-1 dav	Study Visit 8 Dav.50 +/-1 dav	Study Visit 9 Dav.64 +/-2 days	Study Visit 10 Dav.78 +/-2 days	Study Visit 11 Dav.85 +/-2 days	Study Visit 12 Dav.92 +/-2 days	Study Visit 13 Dav.106 +/-2 days	Study Visit 14 Dav.120 +/-2 days	Study Visit 15 Dav.134 +/-2 days	Study Visit 16 Dav.148 +/-2 days	Study Visit 17 Dav.162 +/-2 days	Study Visit 18 Dav.176 +/-3 days	Final Study Visit 19 Dav.246 +/-7 days
Procedures																				
Informed consent	X																			
Demographics	X																			
Medical history	X																			
Administer daratumumab SC		X	X	X	X	X	X	X	X	X	X		X	X	X	X	X	X		
Physical and neuro exam	X											X							X	X
Vital signs	X	X	X	X	X	X	X	X	X	X	X	X	X	X	X	X	X	X	X	X
Height	X																			
Weight	X	X	X	X	X	X	X	X	X	X	X		X	X	X	X	X	X	X	X
12-lead ECG	X																			
CBC	X		X	X	X	X	X	X	X	X	X		X	X	X	X	X	X		X
Comprehensive metabolic panel	X				X				X		X			X		X		X		X
PT/INR, APTT, TSH, B12 level	X																			
Hepatitis B surface antigen and core antibody	X																			
Hepatitis C Virus antibody	X																			
HIV antigen/antibody screen	X																			
Brain MRI	X																		X	
Amyloid PET scan of brain	X																			
Type and screen		X																		
Flow cytometry		X																	X	
Concomitant medications	X	X	X	X	X	X	X	X	X	X	X	X	X	X	X	X	X	X	X	X
Adverse events review		X	X	X	X	X	X	X	X	X	X	X	X	X	X	X	X	X	X	X
Modified Hachinski (MHIS)	X																			
GDS	X																			
CDR	X											X							X	X
MMSE	X											X							X	X
ADAS-Cog	X											X							X	X

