2.3.3 ASSESSMENT OF POTENTIAL RISKS AND BENEFITS

As there are no currently available disease-modifying treatments for AD, there is an adequate rationale to explore the potential efficacy of daratumumab in this small open-label study. The safety profile of daratumumab has been well-characterized in patients with multiple myeloma. Since the AD subjects to be enrolled in this study will be otherwise healthy, without history or evidence of malignancy, cardiac, pulmonary, or other significant medical illnesses or laboratory abnormalities, we expect the risk of adverse hematological effects or infectious complications to be lower than in patients with multiple myeloma. In view of the potential for daratumumab to interfere with the Indirect Antiglobulin Test (indirect Coombs test), and mask detection of antibodies to minor antigens in the subject's serum, type and screen will be sent prior to treatment initiation. To minimize the risk of post-infusion reactions, individuals with a history of asthma or chronic obstructive pulmonary disease will be excluded, and subjects will be premedicated with montelukast 10 mg orally 1 to 3 hours prior to the first dose of daratumumab, diphenhydramine 25 mg orally 1 to 3 hours prior to each dose, acetaminophen 1000 mg orally 1 to 3 hours prior to each dose, and dexamethasone 20 mg orally 1 to 3 hours prior to the first 3 doses, 10 mg orally 1 to 3 hours prior to all subsequent doses, and 4 mg orally the day after each dose. To avoid hepatitis B virus reactivation, subjects with serologic evidence of current or prior hepatitis B infection will be excluded. To prevent herpes zoster reactivation, patients will also be treated with oral acyclovir 400 mg daily beginning the day after the first dose and continuing until 12 weeks after the final dose. After the first dose, subjects will have a CBC performed within 48 hours prior to each subsequent infusion, and the scheduled infusion will be held if there is evidence of clinically significant anemia, neutropenia, leukopenia, or thrombocytopenia. Additional safety laboratory monitoring will include a comprehensive metabolic panel (CMP) every 4 weeks.

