13. The subject is taking or is anticipated to require treatment with an anticoagulant medication, including warfarin, dabigatran, rivaroxaban, apixaban, edoxaban, heparin, or enoxaparin.
14. The subject is taking or is anticipated to require treatment with aspirin at a dose higher than 325 mg daily.
15. The subject has a history of asthma or chronic obstructive pulmonary disease.

16. The subject has had a myocardial infarction, unstable angina, stroke, transient ischemic attack or required intervention for any of these conditions (e.g., coronary artery bypass graft, percutaneous coronary intervention via cardiac catheterization, thrombolytic therapy) within 6 months prior to the screening visit.
17. The subject has had an infection requiring medical intervention within 30 days prior to the screening visit.
18. The subject has serologic evidence of current or prior hepatitis B virus (HBV) infection based on hepatitis B surface antigen or hepatitis core antibody blood tests at the screening visit.
19. The subject has serologic evidence of hepatitis C virus (HCV) infection based on hepatitis C antibody blood test at the screening visit.
20. The subject has serologic evidence of human immunodeficiency virus (HIV) infection based on HIV antigen/antibody test at the screening visit.
21. The subject has a platelet count less than 50,000 per microliter (mL) at the screening visit.
22. The subject has a creatinine clearance less than 30 mL/minute at the screening visit.
23. The subject has a history or evidence of a malignancy (except for adequately treated basal cell or squamous cell skin cancer, in situ cervical cancer, or localized prostate carcinoma) within the 2 years prior to the screening visit.
24. The subject has had any other unstable/uncontrolled medical illness within 12 weeks prior to the screening visit such that, in the judgment of the investigator, participation in the trial would pose a significant medical risk to the subject.
25. The subject has significant visual or auditory impairment, or limited English proficiency, that in the investigator's opinion would preclude collection of outcome measures.
26. The subject has any contraindication to or inability to tolerate brain MRIs (e.g., a pacemaker or any other implanted device or condition that would preclude proximity to a strong magnetic field).

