7 STUDY INTERVENTION AND PARTICIPANT DISCONTINUATION/WITHDRAWAL

7.1 DISCONTINUATION OF STUDY INTERVENTION

Dose Delays and Dose Modifications:

Individual dose modification of daratumumab is not permitted, but dose delay is recommended as the primary method for managing daratumumab-related toxicities.

Daratumumab-Related Toxicity Management:

If any of the following criteria are met and the toxicity is more than expected daratumumab injection must be held to allow for recovery from toxicity. If attribution is unclear, then daratumumab should be held until recovery from toxicity as noted below.

The criteria for a dose delay are:

- Grade 4 hematologic toxicity
- Grade 3 thrombocytopenia with bleeding
- Febrile neutropenia
- Grade 3 or higher non-hematologic toxicities with the following exceptions:
 - Grade 3 nausea that responds to antiemetic treatment within 7 days
 - Grade 3 vomiting that responds to antiemetic treatment within 7 days
 - Grade 3 diarrhea that responds to antidiarrheal treatment within 7 days
 - Grade 3 fatigue that was present at baseline or that lasts for <7 days after the last administration of daratumumab

Grade 3 asthenia that was present at baseline or that lasts for <7 days after the last administration of daratumumab

Administration of daratumumab may be restarted upon recovery from toxicity to Grade 2 or baseline, with the exception that Grade 2 laryngeal edema or Grade 2 bronchospasm must be fully recovered. If daratumumab administration does not commence within the prespecified window of the scheduled administration date (Table 3), then the dose will be considered a missed dose. Administration may resume at the next planned dosing date.

Table 3: Daratumumab-related Toxicity Management

Daratumumab Dosing Frequency	Dose Missed	Dosing Resumption
Weekly	>3 days	Next planned weekly dosing date
Every 2 weeks	>7 days	Next planned every-2-weeks dosing date

Interruption or discontinuation from daratumumab SC infusions does not mean discontinuation from the study, and subjects will be asked to return for scheduled assessments as per the protocol at Visit 11, Visit 18, and Visit 19, if not already completed. If a clinically significant finding is identified (including, but not limited to changes from baseline) after enrollment, the investigator or qualified designee will determine if any change in participant management is needed. Any new clinically relevant finding will be reported as an adverse event (AE).

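### No CBC or CMP is drawn at Visit 1, so the only pre-treatment values for judging treatment-emergent laboratory changes may be up to 60 days old

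*Combined protocol and SAP*

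**What the plan says.** The Schedule of Activities (section 1.3) heads its first column "Screening Dav.-60 to -1". The CBC and CMP rows are marked there and left blank at Visit 1. Section 8.2 agrees on the screening panel: "Blood tests to be collected at the Screening Visit will include complete blood count (CBC), comprehensive metabolic panel (CMP", among other tests. For Day 1 it provides only this: "Blood samples will be obtained at Visit 1, prior to the first infusion, for type and screen and flow cytometry".

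Pre-dose counts begin with the second dose: "After the first dose, subjects will have a CBC performed within 48 hours prior to each subsequent infusion". Section 2.3.3 has the same timing and attaches a consequence: "the scheduled infusion will be held if there is evidence of clinically significant anemia, neutropenia, leukopenia, or thrombocytopenia". The first CMP after Screening is at Visit 4 (Day 22); the remaining on-treatment CMPs are at Visits 8, 10, 13, 15 and 17.

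Three other places bear on how these values are read:

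- Section 8.3.1 includes laboratory test abnormalities among adverse events and refers to change from the baseline condition.
- Section 8.3.4 takes the subject's status at screening as the adverse event baseline and records events from consent onward.
- Section 9.4.4 estimates the proportion of subjects with at least one treatment-emergent adverse event, with an exact 95% interval. Neither section 8.3 nor section 9 defines treatment-emergent.

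Section 7.1 also uses the word baseline: "Administration of daratumumab may be restarted upon recovery from toxicity to Grade 2 or baseline". It does not say which measurement is meant.

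**The concern.** In a single-arm trial, each subject's own pre-treatment value is the only comparator for a laboratory change. Here that value may precede treatment by two months, in subjects aged 55 to 85. Suppose a low count appears at Day 8, or a raised glucose at Day 22. Inclusion criterion 8 bars clinically significant abnormal results at screening, so a clinically significant finding would be new since Screening. Nothing collected shows whether it is also new since the first dose.

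The error can go either way. A change that arose before Day 1 may be counted as treatment-emergent, or a real effect of treatment may be put down to drift before treatment. These are the kinds of change the protocol itself anticipates. Section 2.3.1 tabulates cytopenias with intravenous daratumumab in multiple myeloma and lists high blood sugar among the effects of dexamethasone. By the Day 22 visit subjects have already had three doses of daratumumab, each preceded by dexamethasone 20 mg. A missing Day 1 value cannot be recovered once dosing has started.

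**Working it through.** **Inputs.** All are from section 1.3 unless noted.

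- Screening: Day -60 to Day -1.
- Visit days: Visit 1 = Day 1, Visit 2 = Day 8, Visit 3 = Day 15, Visit 4 = Day 22, Visit 19 = Day 246 (±7 days).
- Dosing visits: 1 to 10 and 12 to 17, which is 16 doses.
- CBC: Screening, Visits 2 to 10, 12 to 17, and 19.
- CMP: Screening, Visits 4, 8, 10, 13, 15, 17, and 19.
- Stated participant duration: up to 44 weeks including screening (section 1.1).

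**Is the 60-day window intended?** Reproduce the stated duration: (60 + 246)/7 = 43.7 weeks, or (60 + 253)/7 = 44.7 weeks at the late edge of the Visit 19 window. Both are close to the stated 44. A 28-day screening window would give (28 + 246)/7 = 39.1 weeks, which is not. The 60 days therefore fits the rest of the plan.

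**Which doses have a CBC at the same visit?** Setting the dosing row against the CBC row, 15 of 16 do. Visit 1 is the only dosing visit without one.

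**Age of the screening sample.** The labels run from -1 to 1 with no Day 0 shown. A sample on Day -s is then s days before Day 1, and its distance to Day d is s + (d - 1), with s from 1 to 60.

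| Interval from Screening sample to | Formula | Shortest | Longest |
|---|---|---|---|
| Dose 1 (Day 1) | s + 0 | 1 day | 60 days |
| First later CBC (Day 8) | s + 7 | 8 days | 67 days |
| First later CMP (Day 22) | s + 21 | 22 days | 81 days |

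If a Day 0 were counted, the maxima would be 61, 68 and 82. Visit windows of ±1 day, and the 48 hours allowed for the CBC, are ignored.

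**CMP at doses 2 and 3.** These doses also rest on the screening CMP, which can be 60 + 7 = 67 days old at dose 2 and 60 + 14 = 74 days old at dose 3.

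**Reading the sections together.** Laboratory abnormalities can be adverse events (8.3.1). The reference point is screening (8.3.4). The endpoint is events that emerge on treatment (9.4.4). Between the reference point and the start of treatment lie up to 60 days with no scheduled CBC or CMP, so the data cannot place a silent change before or after dose 1.

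**With CBC and CMP in the Visit 1 draw.** The pre-treatment comparator becomes a same-day value, and the interval to the first later result becomes 7 days for CBC and 21 days for CMP.

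**The case against.** Much can be said for the plan as written. The pre-dose CBC in section 2.3.3 serves to detect cytopenia during treatment, and no study drug precedes dose 1, so starting the counts at dose 2 has a plain logic. Visit 1 is not unguarded: vital signs, including temperature, are taken before every infusion, adverse events and concomitant medications are reviewed, and section 7.2 allows withdrawal for a newly developed exclusion criterion. Symptomatic changes are partly covered. The 60 days is a permitted maximum, and a subject screened shortly before Day 1 has recent values. All of this stands. What remains uncovered is a laboratory change without symptoms.

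Several stronger readings are tempting but not supported:

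- A reader might infer that the sections contradict each other. They do not: sections 1.3, 2.3.3 and 8.2 agree that counts begin after the first dose.
- A reader might link the missing count to the 40% reaction rate with the first infusion in section 2.3.1. That figure is for intravenous infusion reactions, and nothing in the documents ties those to blood counts.
- A reader might infer that recent infections or cardiovascular events go unchecked for want of these tests. A CBC or CMP does not recheck either history.
- A reader might take 1/15 = 6.7 percentage points as the bias in the adverse event proportion. That is only the step size at N = 15. Because the endpoint counts subjects with one or more events, a misattributed laboratory value changes it only if the subject has no other treatment-emergent event.
- A reader might think the restart rule in section 7.1 turns on this. Since inclusion criterion 8 excludes clinically significant abnormal results at screening, Grade 2 would normally be the operative limit for laboratory toxicity, and the practical effect is probably small.

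**Conclusion.** The point holds as one about baseline measurement. The only pre-treatment CBC and CMP may be up to 60 days old at dose 1, with up to 67 days to the next CBC and up to 81 days to the next CMP. With no control arm and no definition of treatment-emergent, a silent laboratory change in that interval cannot be distinguished from one arising on treatment.

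This rests on three things: nominal visit days with no Day 0; the screening maximum being used, since the documents give no typical interval; and the inference that screening values act as the laboratory baseline. The protocol never names one, but no other pre-dose CBC or CMP exists, and section 8.3.4 sets the adverse event baseline at screening.

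The number of subjects who would be misclassified cannot be estimated from the documents. The primary endpoint and the 7-of-15 criterion are untouched. The contrast between dose 1 and later doses applies to the CBC alone; for the CMP, doses 2 and 3 are in the same position. This is an inexpensive improvement to the safety data, and it cannot be made after dosing begins.

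**What to change.** - Add CBC and CMP to the Visit 1 column of section 1.3 and to the Visit 1 blood draw in section 8.2, taken before premedication.
- State in sections 8.3.4 and 9.4.4 that these Visit 1 values are the laboratory baseline for deciding whether an abnormality is treatment-emergent, and define that term relative to the first dose. Keep the screening values for eligibility.
- Ask the sponsor to state whether the difference between dose 1 and doses 2 to 16 in the timing of the CBC is intended, and which value section 7.1 means by baseline. No dosing rule is proposed here. How an abnormal Visit 1 result would be handled is for the sponsor to decide.

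Cost: one additional CBC and one additional CMP per subject, 15 of each in all, from a draw already scheduled. No extra venepuncture is needed, provided that draw is timed before premedication; section 8.2 says only that it precedes the first infusion.

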8.3 ADVERSE EVENTS AND SERIOUS ADVERSE EVENTS

8.3.1 DEFINITION OF ADVERSE EVENTS (AE)

An adverse event is any untoward medical occurrence in a clinical study subject administered a medicinal (investigational or non-investigational) product. An adverse event does not necessarily have a causal relationship with the treatment. An adverse event can therefore be any unfavorable and unintended sign (including an abnormal finding), symptom, or disease temporally associated with the use of a medicinal (investigational or non-investigational) product, whether or not related to that medicinal (investigational or non-investigational) product. [Definition per International Conference on Harmonisation (ICH)]

This includes any occurrence that is new in onset or aggravated in severity or frequency from the baseline condition, or abnormal results of diagnostic procedures, including laboratory test abnormalities

8.3.2 DEFINITION OF SERIOUS ADVERSE EVENTS (SAE)

A serious adverse event based on ICH and EU Guidelines on Pharmacovigilance for Medicinal Products for Human Use is any untoward medical occurrence that at any dose:

- Results in death
- Is life-threatening (The subject was at risk of death at the time of the event. It does not refer to an event that hypothetically might have caused death if it were more severe.)*
- Requires inpatient hospitalization or prolongation of existing hospitalization
- Results in persistent or significant disability/incapacity

- Is a congenital anomaly/birth defect
- Is a suspected transmission of any infectious agent via a medicinal product
- Is medically important**

***Life-Threatening Conditions:**

Disease progression should not be recorded as an adverse event or serious adverse event term; instead, signs and symptoms of clinical sequelae resulting from disease progression/lack of efficacy will be reported if they fulfill the serious adverse event definition.

****Medical and scientific judgment should be exercised in deciding whether expedited reporting is also appropriate in other situations, such as important medical events that may not be immediately life threatening or result in death or hospitalization but may jeopardize the subject or may require intervention to prevent one of the other outcomes listed in the definition above. These should usually be considered serious. NOTE: DEATH FOR ANY REASON SHOULD BE REPORTED AS A SERIOUS ADVERSE EVENT.**

